### **11.4.2. Analysis Plan**

The analysis for this study is primarily descriptive as the primary objective is to determine the detection rate of bilateral SLNs. The bilateral SLN detection rate will be calculated as the number of patients with bilateral SLN detection divided by the total number of patients. If the bilateral detection rate is at least 80%, we will deem this approach promising in detecting bilateral SLNs.

## **11.5. Secondary Analysis**

### **11.5.1 Analysis Population**

The population for secondary analysis will include all patients in the safety population, i.e. the analysis population plus those women who underwent lymphoseek injection but were removed from the study for any reason.

### **11.5.2 Analysis Plan**

Descriptive statistics will be used to analyze the secondary outcomes. The overall detection rate of sentinel lymph nodes will be calculated as the number of patients with overall SLN detection divided by the total number of patients. To assess the safety of the concurrent use Lymphoseek and Indocyanine Green, we will calculate the number and rate of adverse events. We will describe the location and number of Lymphoseek-positive SLNs by method of detection (pre-operative or intraoperative). We will calculate the number of patients with SLNs found by Lymphoseek and by Indocyanine Green and conduct a McNemar's test (or mid- $p$  McNemar's test) to determine the concordance of Lymphoseek-positive and Indocyanine Green-positive sentinel lymph nodes.

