## PROTOCOL SYNOPSIS

TITLE	Concurrent use of Lymphoseek and Indocyanine Green for sentinel lymph node detection in endometrial cancer – a prospective study
STUDY PHASE	Feasibility
INDICATION	Sentinel lymph node sampling in clinically uterine confined early-stage endometrial cancer
INVESTIGATIONAL PRODUCT OR PROCEDURE	Concurrent use of Lymphoseek and Indocyanine Green in minimally invasive surgery
PRIMARY OBJECTIVE(S)	To determine the detection rate of bilateral sentinel lymph nodes with the concurrent use of Lymphoseek and Indocyanine Green as compared to each agent alone.
SECONDARY OBJECTIVE(S)	
(1) To determine the overall detection rate of sentinel lymph nodes with concurrent use of Lymphoseek and Indocyanine Green
 
(2) To determine location and number of Lymphoseek-positive sentinel lymph nodes preoperatively by single-photon emission computed tomography (SPECT/CT imaging) and intraoperatively by a laparoscopic handheld gamma detection
 
(3) To determine the location and number of Indocyanine Green-positive sentinel lymph nodes by intraoperative infrared fluorescent imaging
 
(4) To determine the concordance of Lymphoseek-positive sentinel lymph nodes with intraoperatively detected Indocyanine Green-positive sentinel lymph nodes, and vice versa, the concordance of Indocyanine Green-positive sentinel lymph nodes with Lymphoseek-positive sentinel lymph nodes.
 
(5) To assess the safety of the concurrent use of Lymphoseek and Indocyanine Green

TREATMENT SUMMARY	
Sentinel lymph node assessment
 
 
- Preoperatively, within 24 hours prior to surgery, the subject will receive in the nuclear medicine suite of Stanford Hospital injections of 0.125 mCi or 0.5 mCi each Lymphoseek into the uterine cervix at 3, 6, 9, and 12 o'clock. Immediate and delayed static planar images will be obtained with and without a transmission source. SPECT-CT of the abdomen and pelvis will be obtained for further characterization.
 
- Subjects will then undergo minimally invasive endometrial cancer surgery. The SPECT/ CT images will be available for review to the surgeon prior to the start of the surgery.
 
- In the operating room, following anesthesia induction, the uterine cervix will be injected with 0.5 mL each of Indocyanine Green at positions of 3, 6, 9, and 12 o'clock.
 
- The surgery will start with the identification and dissection of
 

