### 1.2 Secondary Objectives

- (1) To determine the overall detection rate of sentinel lymph nodes with concurrent use of Lymphoseek and Indocyanine Green;
- (2) To determine the location and number of Lymphoseek-positive sentinel lymph nodes preoperatively by single-photon emission computed tomography (SPECT/CT imaging) and intraoperatively by a laparoscopic handheld gamma detection device and near-infra-red fluorescent imaging;
- (3) To determine the concordance of Lymphoseek-positive sentinel lymph nodes detected by SPECT/CT and/or gamma probe with intraoperatively detected Indocyanine Green-positive sentinel lymph nodes, as well as reverse concordance.
- (4) To assess the safety of the concurrent use of Lymphoseek and Indocyanine Green.

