## 2. BACKGROUND

### 2.1 Study Disease

Endometrial cancer accounts for 50% of all gynecological malignancies in the US. The majority are diagnosed at an early stage. Although clinically locally confined, endometrial cancers may have microscopically spread to lymph nodes; therefore, International Federation of Gynecology and Obstetrics (FIGO) revised the endometrial cancer staging in 1988 to make it a surgical staging system and included a complete pelvic lymphadenectomy [1]. Despite the increased accuracy in staging, complete lymphadenectomy has not been shown in randomized trials to increase progression-free or overall survival [2, 3]. Instead, complete lymphadenectomy carries the risk of increased morbidity, including lymph edema and nerve damage. To reduce this morbidity while maintaining prognostic information, the concept of sentinel lymph node (SLN) sampling has been introduced [4, 5].

Various tracers have been used to identify the first draining lymph node, the sentinel lymph node, and assess for tumor involvement. In the thus-far largest multicenter prospective trial, detection rates for SLNs in minimally invasive surgery for endometrial cancer using Indocyanine Green alone have been reported as only 52% bilaterally and 86% overall [6]. Our own institutional data shows detection rates using Indocyanine Green of 69% and 88%, bilaterally and overall, respectively [7]. If a sentinel lymph node is detected, surgery is restricted to the removal of the SLN and a complete lymphadenectomy is avoided. If no lymph nodes are mapped, current guidelines recommend a complete lymphadenectomy on the side where no sentinel lymph node was detected. Thus, for 30-50% of patients the morbidity of a complete lymphadenectomy cannot be avoided.

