## **4. TREATMENT PLAN**

In this study, the patient will receive cervical injections of Lymphoseek 1 – 24 hours prior to surgery and subsequent SPECT/CT imaging preoperatively. Intraoperatively, following anesthesia induction, Indocyanine Green will be injected into the uterine cervix. Using near-infrared imaging, efferent lymphatic vessels and lymph nodes will be visualized and confirmed by detected radioactivity using a laparoscopic gamma counter. The preoperatively obtained SPECT/CT images will help guide the surgery. The laparoscopic gamma counter will confirm that sentinel lymph node tissue was removed by recording gamma counts before and after lymph node removal.

Subject participation in this study comprises the following:

- Screening**

- Screening begins after informed consent is obtained.
- The screening window is Day 1 to Day 42 after signing of informed consent.
- Screening assesses the subject's eligibility to participate as determined by inclusion/ exclusion criteria.

- Sentinel lymph node assessment**

- Preoperatively, 1 - 24 hrs prior to surgery, the patient will receive in the nuclear medicine suite of Stanford Hospital injections of 0.125 mCi or 0.5 mCi mL each Lymphoseek into the uterine cervix at 3, 6, 9, and 12 o'clock. Then, the patient will undergo SPECT/ CT imaging. Immediate and delayed static planar images will be obtained with and without a transmission source. SPECT-CT of the abdomen and pelvis will be obtained for further characterization. The imaging process will take approximately 1 hour.

- The patient will undergo minimally invasive endometrial cancer surgery. The SPECT/ CT images will be available for review to the surgeon prior to the start of the surgery.
- In the operating room, following anesthesia induction, the uterine cervix of the patient will be injected with about 2.0 mL total of Indocyanine Green. The surgery will start with the identification and dissection of sentinel lymph nodes.
- **Follow up (duration of the study)**
  - The patient will be observed preoperatively after Lymphoseek injection in the nuclear medicine suite and postoperatively in the recovery room for possible allergic reactions or any other adverse events.

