### 9.2 Secondary Outcome

(1) Overall detection (yes/no): For each subject, an assessment will be made of whether there was overall sentinel node detection. A sentinel lymph node will be defined as being detected if it is detected on the pre-operative SPECT/CT imaging scan or intraoperatively using near-infrared imaging or the handheld gamma detection device. If at least one SLN is detected (on any side), then this outcome will be considered a ‘Yes’.

(2) Location and number of SLNs detected by Lymphoseek: The location and number of sentinel lymph nodes detected by Lymphoseek will be assessed. A sentinel lymph node will be defined as being detected by Lymphoseek if it is detected using the pre-operative SPECT/CT imaging scan and/or intraoperatively using the gamma detection device.

(3) Location and number of SLNs detected by Indocyanine Green: The location and number of sentinel lymph nodes detected by Indocyanine Green will be assessed. A sentinel lymph node will be defined as being detected by Indocyanine Green if it is detected intraoperatively using near-infrared imaging only and not by the gamma detection device.

(4) Adverse events and severe adverse events will be monitored and reported.

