### **11.3 Descriptive Statistics and Exploratory Data Analysis**

We will provide descriptive statistics for the study population. The primary and secondary outcomes will be summarized using frequencies and percentages.

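### McNemar's test on patient counts compares the two tracers' detection rates; it does not measure the two-way node concordance that the objective asks for, and no node-level measure is defined

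*Combined protocol and SAP*

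**What the plan says.** The Synopsis, secondary objective 4, asks for concordance of Lymphoseek-positive nodes with ICG-positive nodes and also for "the concordance of Indocyanine Green-positive sentinel lymph nodes with Lymphoseek-positive sentinel lymph nodes". Section 1.2, item 3, repeats this: Lymphoseek-positive nodes on SPECT/CT and/or gamma probe are to be compared "with intraoperatively detected Indocyanine Green-positive sentinel lymph nodes, as well as reverse concordance". Both texts concern nodes, and both ask for two directions.

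The only analysis tied to this objective is in Section 11.5.2. It begins "We will calculate the number of patients with SLNs found by Lymphoseek and by Indocyanine Green" and continues with McNemar's (or mid-p McNemar's) test "to determine the concordance of Lymphoseek-positive and Indocyanine Green-positive sentinel lymph nodes". Section 11.3 adds a general statement: "The primary and secondary outcomes will be summarized using frequencies and percentages". Section 9.2 lists overall detection, location and number of nodes for each tracer, and adverse events. It does not list concordance as an outcome.

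Section 9.2(3) counts a node as detected by ICG "if it is detected intraoperatively using near-infrared imaging only and not by the gamma detection device". In Section 4, however, near-infrared imaging and the gamma counter are used together: "lymph nodes will be visualized and confirmed by detected radioactivity using a laparoscopic gamma counter".

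**The concern.** There are two faults and one related ambiguity.

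- **Quantity.** McNemar's test has as its null hypothesis that the two tracers detect in the same proportion of patients. A large p-value is not evidence that they agree, and a small one is not evidence that they disagree.
- **Unit.** Patient counts cannot show whether the tracers mark the same node. A woman in whom Lymphoseek marks one node and ICG a different one counts as concordant.
- **Definition of ICG-positive.** Section 9.2(3) may mean only that near-infrared imaging is the one modality credited to ICG. Read literally, it removes every gamma-positive node from the ICG count. Only a node seen on SPECT/CT but negative on the gamma probe could then count as shared, and the result could not be interpreted as concordance.

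At stake is the answer to one secondary objective: a p-value would be reported as concordance, while the two proportions requested are not planned.

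**Working it through.** **The plan's own figures.** The plan states no alpha, power or expected agreement for this analysis. Its design figures concern the primary endpoint only. They reproduce (P(X ≥ 24 of 30) is 0.607 at a true rate of 80% and 0.133 at 69%; exact 95% interval for 24/30 is 61.4% to 92.3%) and do not bear on this point.

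**Formulas.** Let a = patients detected by both tracers, b = Lymphoseek only, c = ICG only, d = neither, n = 30.

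- Patient-level agreement = (a + d)/n.
- Exact McNemar p = min{1, 2·P(X ≤ min(b, c))}, with X ~ Binomial(b + c, 0.5).
- Mid-p, for b ≠ c, = exact p − P(X = min(b, c)).

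The cells a and d do not enter the p-value.

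**Inputs.**

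- ICG: Section 2.1 states "Our own institutional data shows detection rates using Indocyanine Green of 69% and 88%, bilaterally and overall, respectively". 0.88 × 30 = 26.4, taken as 26/30 (86.7%).
- Lymphoseek: Section 2.2 says there are no published data in endometrial cancer, so this rate is an assumption. Section 2.1.1 gives 92–96% overall detection for older radiotracers: 0.92 × 30 = 27.6 and 0.96 × 30 = 28.8, taken as 28/30 and 29/30.

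**Test problem.** With these totals, only five tables are possible:

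| Lymphoseek | a/b/c/d | Agreement | Exact p | Mid-p | Detected by either |
|---|---|---|---|---|---|
| 28/30 | 24/4/2/0 | 80% | 0.69 | 0.45 | 30 |
| 28/30 | 25/3/1/1 | 87% | 0.63 | 0.38 | 29 |
| 28/30 | 26/2/0/2 | 93% | 0.50 | 0.25 | 28 |
| 29/30 | 25/4/1/0 | 83% | 0.38 | 0.22 | 30 |
| 29/30 | 26/3/0/1 | 90% | 0.25 | 0.13 | 29 |

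For the first row, 2 × (1 + 6 + 15)/64 = 44/64 = 0.69, and subtracting 15/64 gives a mid-p of 0.45. Within each pair of unequal detection rates, b − c is fixed and b + c falls as agreement rises, so the p-value falls as agreement improves.

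Section 2.1.1 reports combined detection of 90–97% for blue dye plus radiotracer (27 to 29 of 30). Restricting to that range leaves the second, third and fifth rows: agreement 87–93%, exact p 0.25–0.63.

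As a sensitivity case only, let Lymphoseek also be 26/30. The tables then run from 22/4/4/0 to 26/0/0/4. Agreement runs from 22/30 = 73% to 30/30 = 100%, and the exact p is 1.0 throughout.

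**Unit problem.** Take the table 26/2/0/2 and assume one node per tracer in each detected woman. There are then 26 ICG-positive nodes and 26 + 2 = 28 Lymphoseek-positive nodes.

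| Women in whom both tracers mark the same node | Share of ICG nodes that are Lymphoseek-positive | Share of Lymphoseek nodes that are ICG-positive |
|---|---|---|
| 26 | 26/26 = 100% | 26/28 = 93% |
| 13 | 13/26 = 50% | 13/28 = 46% |
| 0 | 0/26 = 0% | 0/28 = 0% |

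The patient table, its 93% agreement and its p-value of 0.50 are the same in all three rows.

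**The case against.** The strongest reply is that this is a small feasibility study with a mainly descriptive analysis. No decision depends on the p-value, the paired table behind McNemar's test already yields patient-level agreement, and location and number of nodes are collected for each tracer. All of that is true, and it limits the consequence. It does not supply the missing measure: separate counts per tracer do not show which nodes are shared, and no numerator, denominator or matching rule is given.

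One can also say that Section 11.5.2 never states the unit of the test, since the sentence names both patients and nodes. Patient level is the natural reading because patients are what is counted. Even at node level, McNemar's test would still compare detection rates and not measure agreement.

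The node example uses arbitrary match counts. Zero matching is a bound rather than a likely result, since both tracers are injected at the same four cervical positions. That is fair, but the example only has to show that the planned output cannot tell the cases apart.

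The ambiguity in Section 9.2(3) has a benign reading, and the two main faults stand without it.

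Two further points stand and belong in the fix. The secondary population in Section 11.5.1 can include women who never received ICG. The surgeon also has the SPECT/CT images before operating, so the two tracers' results are not independent.

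**Conclusion.** The concern holds. Followed as written, Section 11.5.2 would answer a different question from the one in the objectives: whether the tracers' patient-level detection rates differ. At the detection rates assumed from the background sections, patient agreement could be 80–93% with exact p between 0.25 and 0.69, and the p-value falls as agreement improves at given unequal rates. Node concordance among ICG-positive nodes could be anywhere from 0% to 100% with the patient table unchanged.

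The first range rests on the older-radiotracer rates standing in for Lymphoseek; the second rests on one node per tracer per detected woman. The conclusion depends on neither, because it follows from what the test and its unit can measure. The plan should be corrected, but only one secondary objective is affected. The primary endpoint, the 80% rule and the sample size of 30 are untouched.

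**What to change.** 1. In Section 9.2(3), define an ICG-positive node as near-infrared positive whatever its gamma status, and reconcile this with Section 4. Report nodes seen by near-infrared alone as a separate category if wanted.
2. Record SPECT/CT, gamma and near-infrared status for each node, with a location-based rule for matching SPECT/CT nodes to excised nodes.
3. List concordance as an outcome in Section 9.2. In Section 11.5.2, report the proportion of ICG-positive nodes that are Lymphoseek-positive and the reverse, in women who received both tracers. Descriptive proportions are enough; any confidence intervals should allow for several nodes per patient. State that the surgeon could see the SPECT/CT images.
4. Keep McNemar's test only if it is labelled as a comparison of the tracers' patient-level detection rates.

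The cost is wording in two sections, a matching rule, and any per-node fields that the case report forms lack. Those forms are not in the documents, but Section 4 already has gamma counts recorded before and after node removal, and Section 9.2 already collects location and number per tracer. The matching rule should be set before data collection, because node-level pairing may not be recoverable afterwards.

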## **11.6 Sample Size**

### **11.6.1 Accrual estimates**

100 patients are seen annually at our gynecologic oncology clinics and would be considered eligible to participate in this study. We expect 33% to be willing to participate in the study. We anticipate accruing 30 patients over one year/s.

### **11.6.2 Sample size justification**

To address our primary objective, we plan to enroll 30 patients who have concurrent use of lymphoseek and indocyanine green. The sample size is based on a convenience sample from patients routinely followed in the Stanford gynecologic oncology clinic. With 30 participants and assuming a true bilateral detection rate of 80%, the probability of correctly concluding that our approach has an acceptable bilateral detection rate (i.e. 24 patients being detected with bilateral SLNs) is 61%. The probability of incorrectly concluding this (assuming that the true detection rate is 69% - the rate observed with current practice at Stanford) is low at 13%. We will deem the

approach used in this study promising if we observe a bilateral detection rate of at least 80%. The exact 95% confidence interval for the assumed bilateral detection rate of 80% is 61% to 92%.

### **11.6.3 Effect size justification**

The bilateral detection rate using current techniques at Stanford is approximately 69%. Based on this, we would consider a bilateral detection rate of 80% to be promising.

## APPENDICES

### APPENDIX A: Participant Eligibility Checklist

A Participant Eligibility Checklist must be completed in its entirety for each subject prior to registration. The completed, signed, and dated checklist must be retained in the patient's study file and the study's Regulatory Binder.

The study coordinator, treating physician and an independent reviewer must verify that the participant's eligibility is accurate, complete, and legible in source records. A description of the eligibility verification process should be included in the EPIC or other Electronic Medical Record progress note.

Protocol Title:	Concurrent use of Lymphoseek and Indocyanine Green for sentinel lymph node detection in endometrial cancer – a prospective trial
Protocol Number:	
Principal Investigator:	[name]

### II. Subject Information:

Subject Name/ID:
Gender:  Male  Female

### III. Study Information:

SRC Approved  IRB Approved  Contract signed

### IV. Inclusion/Exclusion Criteria

Inclusion Criteria (From IRB approved protocol)	Yes	No	Supporting Documentation*
1. Age 18 or older			
2. Patient has histological diagnosis of cancer of the endometrium.			
3. Patient should have received no prior treatment.			
4. Patient has a clinical negative node status at study entry.			
5. Patient is a candidate for minimal invasive surgery with lymph node assessment.			
6. Eastern Cooperative Group (ECOG)			

performance status of 0-2			
7. If age less than or equal to 55 years, the patient has a negative pregnancy test within 72 hours before administration of Lymphoseek, has been surgically sterilized, or has been postmenopausal for at least 1 year.			
8. Willing and able to provide a written informed consent document for the trial.			
Exclusion Criteria (From IRB approved protocol)			
1. Patient has participated in another investigational drug study within 30 days of scheduled surgery.			
2. Patient has clinical or radiological evidence of metastatic disease.			
3. Patient has a history of a prior loop electrosurgical excision procedure (LEEP) or cone procedure performed on her cervix.			
4. Patient has a history of previous abdominal retroperitoneal surgery or abdominal/pelvic lymphadenectomy.			
5. Patient has a known hypersensitivity to Indocyanine Green and/or Lymphoseek.			
6. The patient has an iodine allergy			
7. The patient is pregnant or lactating.			

\*All subject files must include supporting documentation to confirm subject eligibility.

The method of confirmation can include, but is not limited to, laboratory test results, radiology test results, subject self-report, and medical record review.

